# 11.2.5. Immunological Research Assays

# 11.2.6. Cytokines

Subject sera will be collected for cytokines (such as IL-12p70, IFN- $\gamma$  and TNF- $\alpha$ ) detection and analyses. AlloStim® is designed to activate a Th1 immune response. Measuring IL-12, TNF- $\alpha$  and IFN- $\gamma$  in a subject's sera can provide evidence to support activation and sustainability of a Th1 immune response activated by AlloStim®. In addition, chronic inflammatory adverse events could be attributed to AlloStim® by following these cytokines, especially TNF- $\alpha$ .

When cytokines testing is required, ~5 ml of whole blood is collected in blood tubes provided by the sponsor and incubated for 30 to 60 minutes at room temperature. Tubes will be centrifuged for 15 minutes at ~1000 rcf and the serum will be separated and aliquoted into new pre-labeled tubes. All samples should be labeled with subject study ID, protocol number, protocol day, date and time of collection. Serum samples should be kept at minus 20°C (-20°C) or below until shipped. Samples will be shipped on a dry ice or in a liquid nitrogen dry shipper via overnight courier to:

# 11.2.7. Th1/Th2 Intracellular Staining

AlloStim® priming is designed to increase the number of Th1 cells in circulation. Since IFN-y is a prototypic marker of Th1 cells and IL-4 is a prototypic marker of Th2 cells, the Th1/Th2 balance can be detected by activating T-cells and measuring the expression of IFN- $\gamma$  and IL-4. Th1/Th2 analysis requires ~50 ml of whole blood in blood tubes provided by the sponsor. The PBMC will be isolated from whole blood following the instructions provided by the Sponsor. Briefly, the whole blood tubes should be centrifuged at 1500 rcf for 15 minutes and whitish layer to be collected into new pre-labeled tube. After the cell counting, the separated PBMC will be washed by centrifugation 8 minutes at 402 rcf, and re-suspended in freezing medium to final concentration of  $10 \times 10^6$ /ml. The suspended cells will be aliquoted to  $10^7$ PBMC/vial. All PBMC samples should be labeled with subject study ID, protocol number, protocol day, date and time of collection. PBMC samples should be frozen and stored at -80°C or below until shipping. All PBMC samples will be shipped on a dry ice or in a liquid nitrogen dry shipper via overnight courier to:

#### **DESCRIPTION OF STUDY VISITS** 12.

The following tables summarize all planned assessments, tests, and treatments scheduled to occur as part of this study, including pretreatment evaluations, end of therapy assessments, and follow-up. These assessments will be conducted at the PI clinic and a Sponsor-designated radiology center (imaging, cryoablation and biopsy). Some deviations in the schedule of assessments are allowed as indicated in protocol deviation section 12.1.

### Table 1 Table of Assessments Schedule A-1

| Protocol activity                      | Baseline | ID# 1 | ID# 2 | ID# 3 | Cryoablation | 1# A1 | IV booster #1 | IV booster #2 | CT+biopsy |
|--|----------|-------|-------|-------|--------------|-------|---------------|---------------|-----------|
| Protocol day                           | -14 to-1 | 0     | 7     | 14    | 21           | 28    | 56            | 84            | 91        |
| Informed Consent                       | Х        |       |       |       |              |       |               |               |           |
| Demographics                           | Х        |       |       |       |              |       |               |               |           |
| Inclusion/Exclusion Criteria           | Х        |       |       |       |              |       |               |               |           |
| Medical History                        | Х        |       |       |       |              |       |               |               |           |
| Physical Examination (complete)        | Х        |       |       |       |              |       |               |               |           |
| Physical Examination (brief)           |          | х     | х     | х     |              |       | х             |               |           |
| Vital signs                            | Х        | х     | х     | х     | Х            | х     | х             | х             |           |
| ECOG                                   | Х        |       |       |       |              |       |               |               |           |
| EKG                                    | Х        |       |       |       |              |       |               |               |           |
| CT Scan (head, chest, abdomen, pelvis) | Х        |       |       |       |              |       |               |               |           |
| CT Scan (chest, abdomen, pelvis)       |          |       |       |       |              |       |               |               | х         |
| Cryoablation under US or CT guidance   |          |       |       |       | Х            |       |               |               |           |
| Biopsy                                 | Х        |       |       |       |              |       |               |               | Х         |
| Hematological Profile (CBC)            | Х        |       | х     | х     | Х            | х     | х             | х             | х         |
| Chemistry Profile (CMP)                | Х        |       | х     | х     | Х            | х     | х             | х             | х         |
| Inflammation Biomarkers*               | X        |       | х     | х     | Х            | x     | х             | х             | х         |
| Pregnancy Test (β-HCG)                 | Х        |       |       |       |              |       |               |               |           |
| Coagulation profile (PT, PTT, INR)     | Х        |       |       | х     |              |       |               |               |           |
| Autoimmune Panel**                     |          | х     |       |       |              |       |               |               | Х         |
| HLA engraftment test                   | X        |       |       |       |              |       |               |               | Х         |
| Research blood draw***                 |          | х     |       |       | Х            |       | х             | х             |           |
| Concomitant Medications                | X        | х     | х     | X     | Х            | х     | х             | х             |           |
| Adverse Events                         |          | х     | х     | х     | Х            | х     | х             | х             | Х         |

# Table 2 Table of Assessments Schedule A-2

| Protocol activity                               | Baseline | 1 #OI | ID# 2 | ID# 3 | ID #4 | ID #2 | IV #1 | IV #2 | IV#3 | IV #4 | CT+biopsy |
|---|----------|-------|-------|-------|-------|-------|-------|-------|------|-------|-----------|
| Protocol day                                    | -14 to-1 | 0     | 3     | 7     | 10    | 14    | 21    | 28    | 49   | 77    | 91        |
| Informed Consent                                | Х        |       |       |       |       |       |       |       |      |       |           |
| Demographics                                    | Х        |       |       |       |       |       |       |       |      |       |           |
| Inclusion/Exclusion Criteria                    | Х        |       |       |       |       |       |       |       |      |       |           |
| Medical History                                 | Х        |       |       |       |       |       |       |       |      |       |           |
| Physical Examination (complete)                 | Х        |       |       |       |       |       |       |       |      |       |           |
| Physical Examination (brief)                    |          | Х     | х     | х     | х     | х     | х     | х     | х    | х     |           |
| Vital signs                                     | Х        | х     | х     | х     | х     | х     | х     | х     | х    | х     | Х         |
| ECOG  | Х        |       |       |       |       |       |       |       |      |       |           |
| EKG   | Х        |       |       |       |       |       |       |       |      |       |           |
| CT Scan (4 phase) head, chest, abdomen, pelvis) | Х        |       |       |       |       |       |       |       |      |       |           |
| CT Scan (3 phase) chest, abdomen, pelvis)       |          |       |       |       |       |       |       |       |      |       |           |
| Biopsy  | Х        |       |       |       |       | х     |       |       |      |       | Х         |
| Hematological Profile (CBC)                     | Х        |       | х     | х     |       | х     |       | х     |      | х     | Х         |
| Chemistry Profile (CMP)                         | Х        |       | х     | х     |       | х     |       | х     |      | Х     | Х         |
| Inflammation Biomarkers*                        | Х        |       | х     | х     |       | х     |       | х     |      | Х     | Х         |
| Pregnancy Test (β-HCG)                          | Х        |       |       |       |       |       |       |       |      |       |           |
| Coagulation profile (PT, PTT, INR)              | Х        |       |       |       |       | х     |       |       |      | Х     |           |
| Autoimmune Panel**                              |          | х     |       |       |       |       |       |       |      |       |           |
| HLA test  | Х        |       |       |       |       |       |       |       |      |       | х         |
| Research blood draw                             |          | Х     |       | х     |       | х     |       | х     | х    | х     | Х         |
| Concomitant Medications                         | Х        | х     | х     | x     | х     | x     | X     | X     | x    | X     | Х         |
| Adverse Events                                  |          | X     | x     | x     | х     | x     | x     | x     | x    | x     | х         |

# **12.1.** SCHEDULE DEVIATIONS

Scheduled protocol activities should be conducted on the specified protocol days. In some cases the scheduling may not be able to be followed precisely. For example, subjects may miss appointments causing deviations due to illness, weather, transportation problems or miscommunication. The clinic may experience deviations in scheduling due to lack of available site personnel, lack of available supplies, mechanical or equipment failures. Deviations may also occur due to unavailability of the study drug, due to QC failures or study drug transport problems. In addition, holidays and weekend scheduling may cause conflicts.

If a scheduled protocol appointment is missed for any reason and the study drug has already been shipped, the protocol procedure can be delayed by one or two days, as long as the study drug is delivered within its 72 hours shelf life time. If the study drug cannot be delivered within the 72 hours shelf-life window, then the protocol procedure should be rescheduled for the next available protocol activity day. When rescheduling protocol treatments, the study drug should not be administered within 3 days of a previous study drug administration. Thus, up to a 7 day delay in protocol procedures is allowed for a missed appoint.

For schedule C, the second intratumoral injection after cryoablation (day 17) must occur 3 days +/- 1 day after the ablation procedure.

Schedules for laboratory and research blood tests and follow-up assessments can deviate +/- 3 days from the scheduled protocol days. Schedules for CT scans can deviate +/- 1 week from the protocol days. All protocol deviations should be documented with the reason and the rescheduling clearly stated on a form provided by the Sponsor for this purpose.

If protocol deviations in treatment days occur more than once or occur outside of the allowed deviation windows, the subject will be censored as of the date of the violating deviation for survival analysis.

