## **Brief Description of the Protocol:**

This is a single center, open label study comparing CryoVaxTM personalized anti-tumor vaccine protocol combining the cryoablation of a selected metastatic lesion with intra-lesional immunotherapy with AlloStim® alone. The treatment schedules both have the following steps: (1) priming with intradermal AlloStim®; (2) vaccination combining cryoablation with intratumoral AlloStim® or intravenous AlloStim® dosing in the place of cryoablation; (3) activation with intravenous AlloStim®; and (4) booster with intravenous AlloStim®. All subjects are followed for safety during the dosing period and until 28 days following the last dose (Safety Evaluation Period"). All subjects are continued to be followed for survival after the Safety Evaluation Period.

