## **Statistical Analysis:**

Safety analyses will be performed on the safety population, defined as all subjects in the Intent to Treat (ITT) population that received any dose of study medication. The number of AEs reported will be summarized. Subjects will be censored is still alive at data cut-off or if they withdraw consent. The incidence and percentage of subjects with at least one occurrence of a preferred term will be included, according to the most severe NCI-CTCAE Version 4.03 grade.

Causality (relationship to study drug) will be summarized separately. Duration of AE will be determined and included in the listings along with action taken and outcome.

Laboratory results will be classified according to NCI-CTCAE Version 4.03. Incidence of laboratory abnormalities will be summarized; laboratory results not corresponding to an NCI-CTCAE Version 4.03 terms will not be graded. Laboratory toxicity shifts from baseline to worst grade will also be provided.

Any clinically significant results from physical examination and vital signs measurements will be tabulated.

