In accordance with the 3+3 design, three subjects will be accrued into the first dosing schedule. If during the priming, vaccination and activation steps no ADLT are observed in any of the three subjects, accrual into the next cohort is allowed. If an ADLT occurs in two of the three subjects, no further dosing is allowed. If ADLT occurs in one of the three subjects, three additional subjects will be accrued into the same cohort. If no ADLT occurs within the additional three subjects, accrual into the next cohort can begin. If an ADLT is observed in any of the additional three subjects, no further dose escalation is permitted.

The development of any DLT toxicity in  $\geq$  33% of the accumulated number of subjects in any and all dosing schedules during the Safety Evaluation Period will result in protocol discontinuation.

At the completion of the Safety Evaluation Period for all cohorts, the safety evaluation of Part 1 will be considered completed and all enrollment will be closed. Efficacy evaluation will continue monthly for each subject until death or loss to follow-up.

# Part 2

The safety and efficacy data from Part 1 will be evaluated and the favored schedule advanced to Part 2. In Part 2 of the trial, up to 25 additional subjects may be accrued.

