# **9.2. EXPLORATORY ENDPOINT**

- Correlation of tumor burden by RECIST, pathological response and immune response to Overall Survival (OS).
  - Overall Survival (OS) is evaluated from time of enrollment until death from any cause. Subjects are followed for survival during the trial, as long as they are alive, for 12 months after the last study treatment through follow-up phone calls.
  - Traditionally, oncology investigators have relied upon Response Evaluation Criteria in Solid Tumors (RECIST) to serve as a surrogate to predict clinical benefit. RECIST criteria for clinical outcomes rely upon the assumption that agent activity results in shrinkage of tumor and that enlargement of disease is a result of tumor growth. RECIST is a composite evaluation of response based upon measurements of the changes in tumor size [82]. RECIST criteria have been criticized for not being a reliable method to predict OS benefit for cytotoxic agents [83].

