#### **16.1.6. Exploratory Endpoints**

All data will be summarized using descriptive statistics by dosing schedule. All subjects who received any study medication will be included in the analysis.

If the subject is alive at the end of the follow-up period or is lost to follow-up, OS will be censored on the last date the subject is known to be alive.

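### Sections 12.1 and 14.6 censor or drop subjects at schedule deviations, steroids or anti-cancer therapy, against the OS definition and the all-dosed analysis sets, and nothing says which rule prevails

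*Combined protocol and SAP*

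**What the plan says.** **OS and analysis sets.** Section 9.2: "Overall Survival (OS) is evaluated from time of enrollment until death from any cause". Section 16.1.6: "All subjects who received any study medication will be included in the analysis"; for a subject alive at the end of follow-up or lost, "OS will be censored on the last date the subject is known to be alive". The abstract's Statistical Analysis paragraph has "Subjects will be censored is still alive at data cut-off or if they withdraw consent". Section 16.1.3 analyses safety in everyone who received any dose.

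**Follow-up.** Section 8: "Efficacy evaluation will continue monthly for each subject until death or loss to follow-up". The abstract: "All subjects are continued to be followed for survival after the Safety Evaluation Period".

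**Rules that cut subjects off.**
- Section 12.1 applies when treatment-day deviations are repeated, or when they "occur outside of the allowed deviation windows, the subject will be censored as of the date of the violating deviation for survival analysis". Its examples of causes include "subjects may miss appointments causing deviations due to illness, weather, transportation problems or miscommunication", as well as site, supply and calendar problems.
- Section 14.6, anti-cancer therapy in the Study Period: the subject's data are dropped, safety data are reported but censored at the treatment date, and a further subject is accrued.
- Section 14.6, systemic steroids in the Study Period: the subject is dropped and the data are censored from the first steroid day.
- Section 14.6, immunosuppressants: the subject is censored for analysis, but adverse events must still be reported.
- Section 16.1: subject data are censored at steroid administration.

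**Infusion reactions.** For Grades 3 and 4, section 15.4 directs steroids as medically indicated and keeps the subject in follow-up. Its Grade 2 text links dropping to dexamethasone.

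**The concern.** Two analysts working faithfully from this document could report different OS data and different adverse event tables for the same subjects. One would follow 9.2 and 16.1.6 and count every death in every dosed subject. The other would follow 12.1, 14.6 and 16.1, discard deaths after a trigger, and remove some subjects altogether. No section ranks the rules or calls one a sensitivity analysis.

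The choice is not neutral. Illness, toxicity that needs steroids, and need for other cancer treatment can all be related to the risk of death. Censoring at such events assumes that those cut off have the same later risk as those who remain. Dropping them selects the analysed group on something that happened after treatment began.

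OS is exploratory here, but it is the outcome against which RECIST, pathological response and immune response are to be correlated (9.2). Part 1 efficacy data also feed the choice of schedule for Part 2 (section 8). With three subjects per schedule in Part 1, removing one removes a third of that schedule's data.

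**Working it through.** The plan gives no OS assumption, event count or trigger rate (16.1.8 says only that at least three subjects per schedule was considered sufficient). There is no planned figure to reproduce, so the check is mainly textual.

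**Step 1: the rules side by side.**

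| Trigger | Action | Endpoint named? | Conflicts with |
|---|---|---|---|
| Second or out-of-window treatment-day deviation (12.1) | Censor | Yes, survival | OS to death from any cause (9.2); censoring reasons listed in 16.1.6 |
| Anti-cancer therapy in Study Period (14.6) | Drop data, censor safety data, replace | Safety only | All-dosed sets (16.1.3, 16.1.6) |
| Systemic steroids (14.6) | Drop subject, censor data | No | All-dosed sets; 15.4 for those given steroids for a Grade 3/4 reaction |
| Dexamethasone (15.4, Grade 2) | Drop subject, censor data | No | 14.6, which drops for any systemic steroid |
| Immunosuppressants (14.6) | Censor for analysis | No | Unclear: reach to OS and AE tables not stated |
| Steroids (16.1) | Censor subject data | No | Unclear: same |

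Two details matter. The 12.1 rule does not exempt a second deviation that lies inside the permitted delay of up to 7 days. Also, censoring keeps a subject in an analysis set and discards later deaths, whereas dropping takes the subject out. Only dropping conflicts with the all-dosed sets.

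**Step 2: can the direction of bias be stated?** A simple model tests this. It illustrates sign and is not an estimate. Assumptions:
- True median OS is 5.3 months (placebo arm of the TAS-102 trial described in section 6.2).
- Death hazard is λ before a trigger.
- Triggers occur at constant rate r from Day 0 to Day 84, the last scheduled A-1 dose: W = 84/30.4375 = 2.76 months.
- A fraction f = 15% of subjects trigger, where f = r/(r+λ) × (1 − exp(−(r+λ)W)).
- After the trigger, a share q has hazard HR × λ and the rest keep λ.
- λ is solved so that overall true survival at 5.3 months is 0.5.

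If triggered subjects are censored, the Kaplan-Meier median is ln2/λ. If they are dropped, survival after W among the rest is exp(−λt − rW)/(1 − f), so the median is (ln2 − ln(1 − f) − rW)/λ.

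For a non-prognostic trigger, λ = 0.693/5.3 = 0.1308 and rW = 0.1956. Censoring gives 0.693/0.1308 = 5.30. Dropping gives (0.693 + 0.1625 − 0.1956)/0.1308 = 5.05.

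| Later hazard (f = 15%, truth 5.3 months) | Censored median | Dropped median |
|---|---|---|
| Unchanged | 5.30 | 5.05 |
| Doubled in half of triggered subjects | 5.58 | 5.33 |
| HR 0.77 in all (regorafenib figure, section 6.2.7) | 5.13 | 4.87 |

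Censoring gives no shift, an upward shift or a downward shift. Dropping gives a downward shift, almost none, or a larger downward shift. Dropping moves the median even when the trigger is non-prognostic, because a subject must survive long enough to trigger.

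**Step 3: compare with sampling error.** The favored schedule can hold 3 + 25 = 28 subjects. With a true median of 5.3 months, exponential survival and no censoring, the sample median of 28 subjects lies between about 3.0 and 8.6 months in 95% of simulated trials. That is far wider than any shift in the table.

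**The case against.** The strongest reply is that these rules can be read together. Section 16.1.6 says when OS is censored but does not say that nothing else censors it, so 12.1 can be taken as an added rule. This is fair as far as it goes: a reader might infer that 16.1.6 excludes other reasons, and its words do not. It still leaves the statistical section silent about a survival rule placed under scheduling, and leaves that rule at odds with an endpoint that runs to death from any cause. The abstract's censoring sentence stands in a safety paragraph and does not name OS, so little weight rests on it.

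Several other parts of the reply stand:
- Only 12.1 names survival analysis. The immunosuppressant rule in 14.6 and the steroid rule in 16.1 are ambiguous, not demonstrably OS rules.
- The follow-up statements in section 8 and the abstract describe conduct. They are compatible with censoring in analysis, though not with dropping a subject from the study.
- Steroids in 15.4 are given as medically indicated, so the conflict with 14.6 concerns subjects who receive them, not everyone with a Grade 3 or 4 reaction.
- OS is exploratory and descriptive, no test or power depends on it, and section 8 names no OS criterion for choosing the schedule. (Section 11.2.4 calls OS the primary endpoint, contrary to 9.1; this point does not rely on that.)

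A reader might also infer that dose-limiting toxicities after a trigger vanish from the 3+3 or 33% rules. No section says those rules use censored data. Section 15.3.1 requires reporting of all adverse events in the reporting period, 13.2 follows study-related toxicity to resolution or stabilisation, and 14.6 requires reporting after immunosuppressants.

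**Conclusion.** The point holds as a conflict of rules that should be fixed before analysis. Section 12.1 censors survival for reasons outside the OS definition and the 16.1.6 list. The dropping rules in 14.6 conflict with the all-dosed sets and, for subjects given steroids for a Grade 3 or 4 infusion reaction, with 15.4. The Grade 2 text in 15.4 and the steroid rule in 14.6 also differ on which steroid leads to dropping. The remaining rules in 14.6 and 16.1 are ambiguous about OS and adverse event tables.

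Followed as written, these rules can bias the exploratory OS results and their correlations. It is tempting to say that they inflate survival, but the documents do not support a direction or a size. They give no trigger rates, the two mechanisms act differently, and the illustrated medians fall on both sides of the truth. Those medians depend on an assumed trigger fraction, exponential survival and assumed later hazards. The conclusion rests on the text, not on them.

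**What to change.** In 12.1, 14.6 and 16.1, state that treatment-day deviations, steroids, immunosuppressants and anti-cancer therapy are recorded with date and reason, but do not censor OS in the main analysis or remove a dosed subject from the OS or safety sets. Then:
- Apply the 16.1.6 OS rule, plus consent withdrawal, to every dosed subject.
- Tabulate adverse events through the Safety Evaluation Period regardless of these events.
- Keep replaced subjects in the sets; replacements add to them.
- Present any OS version censored at these events as a labelled sensitivity analysis.
- Reconcile 14.6 and 16.1 with 15.4, 16.1.3 and 16.1.6, including the difference between dexamethasone and any systemic steroid. The clinical rule is for the sponsor and investigators.

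A separate inconsistency also needs their attention. Section 14.6 bars anti-cancer therapy for 140 days, while section 6.2 permits salvage regorafenib or TAS-102 after the Safety Evaluation Period. With all scheduled boosters given, that period ends at Day 84 + 28 = 112 (A-1) or Day 77 + 28 = 105 (A-2).

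The cost is wording: survival calls and adverse event reporting are already planned. The downside is that reported OS may look less favourable and will include the effect of later therapy.
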